#### 3.1.2 Secondary Objectives

- To determine if the difference in response to therapy between treatment arms by Month 6 differs among subjects with or without HIV infection
- To determine the impact of multiple BPG injected doses on subject compliance with study product and adherence to the corresponding scheduled visits
- To determine the incidence and manifestations of the Jarisch-Herxheimer reaction among subjects treated for early syphilis with BPG
- To collect prospective data up to Month 12 on the serological response to therapy in subjects treated for early syphilis with either BPG regimen
- To compare epidemiological characteristics of early syphilis among subjects with or without HIV infection

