## 11 STATISTICAL CONSIDERATIONS

### 11.1 Study Hypotheses

The primary objective of the study is to compare the serological response to therapy in subjects with early (primary, secondary, or early latent) syphilis treated with BPG 2.4 MU once or weekly for three successive weeks. In particular, the objective is to demonstrate noninferiority of the one-dose regimen compared to the three-dose regimen and to also assess noninferiority within the HIV status subgroups (HIV-infected and HIV-uninfected subjects). See Section 11.4.4 for the definition of serological response.

The null hypothesis for the primary objective is that the difference in serological response rate between the three-dose and one-dose groups is at least 10%, and the alternative hypothesis is that the difference in response rates is less than 10%. The null and alternative hypotheses for the secondary HIV status subgroup objective are defined similarly.

Note that tests will be performed and p-values will be reported for secondary analyses for informational purposes and not to make definitive claims. The study is intended and designed to formally test the primary hypothesis only, and so no corrections for multiplicity are planned.

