### 11.2 Sample Size Considerations

Sample size calculations were performed using PASS 2008 and SAS 9.4. The following parameters were used for determining the required sample size for the primary objective:

- 1:1 allocation ratio between one-dose and three-dose arms
- Test the difference in response rate between the one-dose and three-dose arms (Farrington-Manning test, unadjusted for HIV status)
- Null hypothesis response rate in one-dose arm: 0.688
- Null hypothesis response rate in three-dose arm: 0.788
- Alternative hypothesis response rate in both arms: 0.788
- One-sided 0.05 alpha level

To achieve 80% power for the primary noninferiority comparison, 420 evaluable subjects (210 in each treatment arm) are needed. It is assumed that 25% of subjects will be ineligible for the primary analysis, and so 560 enrolled subjects are needed to reach the target of 420 evaluable subjects.

The study is not powered to assess the secondary noninferiority comparisons in the HIV status subgroups. As an illustration, power calculations were performed to assess the power available for these subgroup analyses using a sample size of 420. The following parameters were used for the calculations:

- Test the difference in response rate between the one-dose and three-dose arms within each HIV status stratum.
- Null hypothesis response rate in one-dose arm: 0.738 (HIV-infected); 0.638 (HIV-uninfected)
- Null hypothesis response rate in three-dose arm: 0.838 (HIV-infected); 0.738 (HIV-uninfected)
- Alternative hypothesis response rate in both arms: 0.838 (HIV-infected); 0.738 (HIV-uninfected)
- One-sided 0.05 alpha level
- 280 evaluable subjects in the HIV-infected stratum (140 in one-dose arm, 140 in three-dose arm).
- 140 evaluable subjects in the HIV-uninfected stratum (70 in one-dose arm, 70 in three-dose arm).

The HIV-infected noninferiority comparison has 72% power, and the HIV-uninfected noninferiority comparison has 38% power.

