### 11.4.4 Efficacy Analysis Plan

#### 11.4.4.1 Primary Efficacy Analysis

For the primary analysis, serological response to therapy by Month 6 will be defined as follows:

- 4-fold or greater decline in RPR titer by Month 6 compared to baseline, OR
- RPR-negative by Month 6 (i.e., seroreversion).

For the primary analysis, subjects who do not meet either of the above criteria by Month 6 will be classified as not experiencing serological response. If a subject has an observed serological response prior to meeting one of the Evaluable analysis population exclusion criteria, the subject will be included in the analyses as a responder. For subjects who have received BPG through the study and subsequently require retreatment for syphilis infection (i.e., per the local clinic's standard protocols), data collected following retreatment will not be used for analyses. Exploratory analyses of the primary outcome will consider alternative classifications of subjects (see Section 11.4.4.2).

For the comparison of efficacy of one dose versus three doses of BPG 2.4 MU, the number and proportion of subjects with serological response will be summarized overall and by treatment.

The point estimates for the treatment-specific proportions and difference in proportions as well as corresponding 95% confidence intervals will be reported. A hypothesis test will be conducted using the Farrington-Manning test at the 5% one-sided level of significance to formally compare the treatment arms. The primary analysis will be performed in the ITT analysis population and repeated as a secondary analysis in the mITT and the Evaluable analysis populations.

As the ITT analyses will include subjects who may not have adequate serological data to determine their response status for any reason, the response will need to be imputed. Multiple methods for imputation will be explored (e.g., Last Observation Carried Forward); details will be provided in the Statistical Analysis Plan.

As a secondary corroborative analysis, the Cochran-Mantel-Haenszel Chi-square test will be used to compare the two treatment arms with respect to response rate across HIV status subgroups (HIV-infected, HIV-uninfected). The Breslow-Day test for the homogeneity of odds ratios will be used to determine if the difference between the two treatment groups with respect to response rates varies by HIV status.

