#### **11.4.4.2 Secondary Efficacy Analysis**

The secondary efficacy analyses will be performed in the ITT and Evaluable analysis populations. For subjects who have received BPG through the study and subsequently require retreatment for syphilis infection (i.e., per the local clinic's standard protocols), data collected following retreatment will not be used for analyses.

For the comparison of efficacy of one dose versus three doses of BPG 2.4 MU by Month 6 in each of the HIV status subgroups, the number and proportion of subjects with serological response will be summarized overall and by treatment within each HIV status subgroup. The point estimates for the treatment-specific proportions and difference in proportions as well as corresponding 95% confidence intervals will be reported. For each HIV status subgroup, a hypothesis test will be conducted using the Farrington-Manning test at the 5% one-sided level of significance to formally compare the treatment arms.

The analyses comparing one dose versus three doses by Month 12, overall and within HIV status subgroups, will follow similarly to the above. In addition, geometric mean titers and fold declines from baseline will be summarized by time-point for each treatment group, overall and within HIV status subgroups.

For the comparison of compliance between the one dose and three dose groups, the number and proportion of subjects who receive all assigned doses within the assigned visit windows will be summarized overall and by treatment. The point estimates for the treatment-specific proportions and difference in proportions as well as corresponding 95% confidence intervals will be reported. A hypothesis test will be conducted using a Chi-square test at the 5% two-sided level of significance to formally compare the treatment arms.

Demographic, sexual history, and other characteristics of subjects will be presented overall and within HIV status subgroups at baseline and throughout follow-up. HIV status subgroups will be compared with respect to epidemiological characteristics using the Pearson Chi-square test for categorical measures and the t-test for independent samples or Wilcoxon rank sum test for continuous measures.

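### Breslow-Day tests odds ratios, but the protocol uses it to judge whether the difference in response rates varies by HIV status; the effect is small, and a contrast of the two rate differences with its interval should be added

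*Protocol*

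**What the plan says.** The first secondary objective (section 3.1.2) is "To determine if the difference in response to therapy between treatment arms by Month 6 differs among subjects with or without HIV infection".

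Section 11.1 sets the primary null hypothesis as "the difference in serological response rate between the three-dose and one-dose groups is at least 10" percent, and adds that "The null and alternative hypotheses for the secondary HIV status subgroup objective are defined similarly". So the trial's effect measure, overall and by HIV status, is a difference in response rate with a 10-point margin.

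Section 11.4.4.2 keeps to that scale within each HIV subgroup. It plans "The point estimates for the treatment-specific proportions and difference in proportions as well as corresponding 95% confidence intervals will be reported", and then "For each HIV status subgroup, a hypothesis test will be conducted using the Farrington-Manning test at the 5% one-sided level of significance".

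For variation of the effect by HIV status, section 11.4.4.1 names one test: "The Breslow-Day test for the homogeneity of odds ratios will be used to determine if the difference between the two treatment groups". The rest of that sentence makes clear that the outcome compared is the response rate and that the grouping is HIV status. The test stands next to a Cochran-Mantel-Haenszel test, in a paragraph introduced as secondary and corroborative. No significance level is given for it.

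**The concern.** The sentence in section 11.4.4.1 names one quantity, the odds ratio, and claims to settle another, the difference in response rates. The two answers agree in general only if the arms do not differ or if the strata share the same underlying response rate. The protocol assumes that the strata do not share it. In section 11.2 the line reads "Alternative hypothesis response rate in both arms: 0.838 (HIV-infected); 0.738 (HIV-uninfected").

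A pattern that is homogeneous in odds ratios can therefore be heterogeneous in rate differences, and the reverse. The test also returns only a p-value. With 140 and 70 subjects per arm in the two strata, a non-significant result could be taken to mean that the effect does not vary by HIV status, although variation larger than the 10-point margin would remain possible.

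**Working it through.** **Inputs (section 11.2).** Response rates under the alternative, both arms: 0.838 HIV-infected, 0.738 HIV-uninfected. One-dose rates under the null: 0.738 and 0.638. Evaluable subjects per arm: 140 HIV-infected, 70 HIV-uninfected. Noninferiority tests at one-sided 0.05. For the heterogeneity tests I assume two-sided 5%.

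**The protocol's own figures first.** With the unpooled approximation, power = Φ(0.10/SE − 1.645), where SE = √(2p(1−p)/n).
- HIV-infected: SE = √(2 × 0.838 × 0.162/140) = 0.0440, power 73.4%.
- HIV-uninfected: SE = √(2 × 0.738 × 0.262/70) = 0.0743, power 38.2%.

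The Farrington-Manning version, with the variance restricted to the null, gives 72.4% and 38.2% against the stated 72% and 38%. For the primary comparison it gives 80.3% at 210 per arm against the stated 80%. The stated figures reproduce.

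**Equal rate differences, unequal odds ratios.** Take the protocol's null pairs, a 10-point deficit in each stratum:
- HIV-infected: (0.738/0.262)/(0.838/0.162) = 2.817/5.173 = 0.545
- HIV-uninfected: (0.638/0.362)/(0.738/0.262) = 1.762/2.817 = 0.626

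**Equal odds ratios, unequal rate differences.** Apply 0.545 to both strata. HIV-infected falls from 0.838 to 0.738, a deficit of 10.0 points. HIV-uninfected has odds 0.5445 × 2.817 = 1.534, so a rate of 1.534/2.534 = 0.605 and a deficit of 13.3 points. A pattern that Breslow-Day treats as homogeneous sits at the margin in one stratum and beyond it in the other.

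**How often this matters.** Simulation of the actual Breslow-Day test and of a Wald test on the difference between the two rate differences, 200,000 trials per scenario (repeat runs differed by about 0.1 point). Three-dose rates are 0.838 and 0.738 throughout.

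| One-dose minus three-dose (HIV-infected, HIV-uninfected) | Breslow-Day rejects | Rate-difference test rejects |
|---|---|---|
| 0, 0 | 5.2% | 5.3% |
| −5, −5 | 5.4% | 5.2% |
| −10, −10 | 6.0% | 5.2% |
| +10, +10 | 12.3% | 5.3% |
| −10, 0 | 24% | 21% |
| 0, −10 | 16% | 21% |
| −15, 0 | 43% | 39% |
| 0, −15 | 29% | 39% |

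In the first four rows the rate differences are equal, so 5% is the target; the last four show power.

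**Hand check of the −10, −10 row.** The log ratio of the odds ratios is ln(0.5445/0.6257) = −0.139. Its variance is the sum of 1/(n p(1−p)) over the four cells: 0.0369 + 0.0526 + 0.0619 + 0.0739 = 0.2253, so SE = 0.475 and the standardised shift is 0.29. The two-sided rejection rate is Φ(0.29 − 1.96) + Φ(−0.29 − 1.96) ≈ 6.0%, as simulated.

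**Precision of the missing contrast.** The strata are independent, so the difference between the two rate differences has

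SE = √(2 × 0.838 × 0.162/140 + 2 × 0.738 × 0.262/70) = √(0.00194 + 0.00552) = 0.0864.

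The 95% half-width is 1.96 × 0.0864 = 16.9 points. A true contrast of (1.96 + 0.84) × 0.0864 ≈ 24 points would be needed for 80% power. If all 560 enrolled subjects were analysed in the same 2:1 split at the same rates (an assumption), the half-width would be 16.9 × √(420/560) = 14.7 points, still wider than the margin.

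**The case against.** Four points on the other side carry weight.

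- **The subgroup analysis is on the right scale.** A reader might infer that the plan gives no estimate of how the effect differs by HIV status, or that the whole HIV objective is answered on the wrong scale. The protocol does not support either reading. Section 11.4.4.2 reports each subgroup's rate difference with a 95% interval and tests it with Farrington-Manning. The contrast is one planned difference minus the other, and its interval can be derived from the two planned ones. What is missing is only that contrast, named and with its own interval.
- **The test is conventional where it stands.** Breslow-Day is the usual homogeneity check beside Cochran-Mantel-Haenszel, and section 3.1.2 does not itself fix a scale. This stands as a reason to keep the test. It does not rescue the sentence in section 11.4.4.1, which speaks of response rates.
- **No decision depends on it.** Section 11.1 makes secondary p-values informational, and section 11.2 says that the subgroup comparisons are not powered. It would be wrong to infer that the primary noninferiority conclusion or the sample size is affected.
- **Neither test is uniformly better.** Breslow-Day loses power for a deficit in HIV-uninfected subjects only and gains a little for one in HIV-infected subjects only. The 12.3% row needs the one-dose arm to be 10 points better in both strata, which lies outside the planning assumptions. The numbers do not support an inference that Breslow-Day must be removed.

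The SAP is not shown here and may name the contrast. That would supply the estimate but would leave the protocol sentence misdescribing what its test determines.

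**Conclusion.** The point holds as a mismatch of scale in one sentence, with a small practical effect. Section 11.4.4.1 uses an odds-ratio test to decide a question about rate differences, and at the protocol's stratum rates the two are not equivalent. The false-signal rate at a common deficit equal to the margin is about 6% instead of 5%. Power for a one-stratum deficit of 15 points differs by 10 points against Breslow-Day or 4 points in its favour, depending on the stratum.

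The more useful gain is in reporting. A half-width of about 17 points shows at once how little the trial can rule out about variation by HIV status, and a lone p-value does not.

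These figures rest on the protocol's assumed rates, on 140 and 70 evaluable subjects per arm, and on a two-sided 5% level that the protocol does not state.

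**What to change.** For the first secondary objective, name as the analysis the HIV-infected rate difference minus the HIV-uninfected rate difference by Month 6, with its 95% confidence interval. Keep Breslow-Day as a supplement to the Cochran-Mantel-Haenszel test, describe it as a check on the odds-ratio scale, and state its significance level.

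The cost is a sentence or two in section 11.4.4.1 or the SAP and trivial programming. No new data are needed, and neither the sample size nor the primary analysis changes.

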#### **11.4.4.2 Secondary Efficacy Analysis**

The secondary efficacy analyses will be performed in the ITT and Evaluable analysis populations. For subjects who have received BPG through the study and subsequently require retreatment for syphilis infection (i.e., per the local clinic's standard protocols), data collected following retreatment will not be used for analyses.

For the comparison of efficacy of one dose versus three doses of BPG 2.4 MU by Month 6 in each of the HIV status subgroups, the number and proportion of subjects with serological response will be summarized overall and by treatment within each HIV status subgroup. The point estimates for the treatment-specific proportions and difference in proportions as well as corresponding 95% confidence intervals will be reported. For each HIV status subgroup, a hypothesis test will be conducted using the Farrington-Manning test at the 5% one-sided level of significance to formally compare the treatment arms.

The analyses comparing one dose versus three doses by Month 12, overall and within HIV status subgroups, will follow similarly to the above. In addition, geometric mean titers and fold declines from baseline will be summarized by time-point for each treatment group, overall and within HIV status subgroups.

For the comparison of compliance between the one dose and three dose groups, the number and proportion of subjects who receive all assigned doses within the assigned visit windows will be summarized overall and by treatment. The point estimates for the treatment-specific proportions and difference in proportions as well as corresponding 95% confidence intervals will be reported. A hypothesis test will be conducted using a Chi-square test at the 5% two-sided level of significance to formally compare the treatment arms.

Demographic, sexual history, and other characteristics of subjects will be presented overall and within HIV status subgroups at baseline and throughout follow-up. HIV status subgroups will be compared with respect to epidemiological characteristics using the Pearson Chi-square test for categorical measures and the t-test for independent samples or Wilcoxon rank sum test for continuous measures.

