### **6.4 Assessment of Subject Compliance with Study Intervention/Investigational Product**

All BPG injections will be directly observed by the administering clinician. Compliance with study product for all subjects will be defined as whether subjects receive all assigned doses within the assigned visit windows.

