### 11.4.1 Analysis Populations

Intent-to-Treat (ITT) Population: This analysis population includes all randomized subjects.

Modified Intent-to-Treat (mITT) Population: This analysis population includes all randomized subjects who are eligible at the baseline visit and whose TPPA result is positive at the baseline visit and/or at Visit 5 (Month 3), if repeat testing was performed.

Safety Population: This analysis population includes all randomized subjects who received at least one dose of study treatment.

Evaluable Population: This analysis population includes all randomized subjects who are eligible at the baseline visit, have a known HIV status determined at or before the baseline visit, have positive TPPA results at the baseline visit and/or Visit 5 (Month 3) (if repeat testing was performed), received all assigned doses of BPG, have adequate RPR titer data available at baseline and applicable follow-up visit(s), and (for HIV-uninfected subjects only) HIV-uninfected status persists through applicable follow-up visit(s).

If a subject receives antibiotic(s) active against *T. pallidum* for reasons other than syphilis between enrollment and the applicable follow-up visit(s), the subject will be included in ITT analyses but excluded from Evaluable analyses. If a subject receives antibiotic(s) active against *T. pallidum* between enrollment and the applicable follow-up visit(s) due to local RPR testing results, the subject will be included in all analyses.

A blinded case review committee will review subjects' data to determine if treatment with drug(s) known to be active against *T. pallidum* for reasons other than syphilis infection excludes the subject from the Evaluable analysis population.

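### The Evaluable version of the compliance comparison removes missed doses before compliance is measured and so overstates three-dose compliance; the ITT version, also planned, is sound

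*Protocol*

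**What the plan says.** Section 11.4.4.2 of the protocol, headed Secondary Efficacy Analysis, begins with a general rule on populations: "The secondary efficacy analyses will be performed in the ITT and Evaluable analysis populations". It then covers serological response by HIV subgroup and by Month 12, dosing compliance, and characteristics by HIV status.

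For compliance, "the number and proportion of subjects who receive all assigned doses within the assigned visit windows will be summarized overall and by treatment", with 95% confidence intervals for each arm and for the difference. Then: "A hypothesis test will be conducted using a Chi-square test at the 5% two-sided level of significance to formally compare the treatment arms". No population is named for this comparison and no exception is made to the opening sentence.

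Section 6.4 defines the outcome: "Compliance with study product for all subjects will be defined as whether subjects receive all assigned doses within the assigned visit windows". The secondary outcome list in section 3.2.2 uses the same definition.

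Section 11.4.1 defines the two populations. For ITT: "This analysis population includes all randomized subjects". Evaluable subjects must, among other conditions, have "received all assigned doses of BPG" and have adequate RPR titers at baseline and follow-up. Evaluable membership carries no condition on dosing windows.

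**The concern.** One of the secondary objectives in section 3.1.2 is to learn what multiple injected doses do to compliance. The obvious cost of a three-dose course is that some subjects do not return for dose two or three. A population that requires all doses to have been received takes those subjects out before anything is counted. What is left measures punctuality among people who completed the course.

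The effect is lopsided. Arm 1 is dosed only at Visit 1, the visit of randomization, so the filter barely touches it. Arm 2 must also be dosed at Visits 2 and 3, so nearly all of the removed non-compliance is Arm 2's. The Evaluable estimate of the difference, its confidence interval and its chi-square test would all lean towards no difference between regimens. The report would then carry two compliance results that disagree for a purely definitional reason, and the protocol does not say which of them answers the objective.

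**Working it through.** **Inputs from the protocol**
- Compliant means all assigned doses received and all of them in window (6.4).
- Evaluable requires all assigned doses received, with no window condition (11.4.1).
- ITT is everyone randomized (11.4.1).
- Arm 1 is dosed at Visit 1 only; Arm 2 at Visits 1, 2 and 3 (Appendix A, footnote on BPG administration).
- 560 subjects enrolled 1:1 (5.3.1, 11.2), so 560/2 = 280 per arm.

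The protocol states no expected compliance rate and no power for this comparison, so there is no figure of its own to reproduce.

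**Formula.** Within an arm, let *c* be the probability that all assigned doses are received, and *w* the probability that all are in window given that all were received.
- ITT compliance = *c* × *w*
- Evaluable compliance ≈ *w*, because only subjects counted in *c* remain
- Ratio, Evaluable to ITT = 1/*c*; overstatement = *w*(1 − *c*)

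In terms of the proportion missing a dose (*m*) and the proportion with all doses but at least one out of window (*l*), ITT compliance is 1 − *m* − *l* and Evaluable compliance is (1 − *m* − *l*)/(1 − *m*).

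**Arm 2, assumed rates, with Arm 1 taken as fully compliant**

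| *m* | *l* | ITT | Evaluable | Gap to Arm 1, ITT | Gap to Arm 1, Evaluable |
|---|---|---|---|---|---|
| 10% | 5% | 85% | 0.85/0.90 = 94.4% | 15 points | 5.6 points |
| 20% | 10% | 70% | 0.70/0.80 = 87.5% | 30 points | 12.5 points |

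As counts for the first row: of 280 in Arm 2, 28 miss a dose and 14 are dosed out of window, leaving 238 compliant. ITT gives 238/280 = 85%. Evaluable starts from at most 280 − 28 = 252 and gives 238/252 = 94.4%. Of the 42 non-compliant subjects, 28 (two thirds) are never counted.

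**Range.** For *c* from 0.70 to 0.95 and *w* from 0.90 to 1.00, the overstatement *w*(1 − *c*) runs from 0.90 × 0.05 = 4.5 points to 1.00 × 0.30 = 30 points. If every dose given is in window (*w* = 1), Evaluable shows 100% whatever share of Arm 2 missed a dose.

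These figures use only the all-doses condition. The other Evaluable conditions are ignored. The need for adequate follow-up titers probably selects subjects who attend visits, which would push the same way, but the protocol gives nothing with which to size it.

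**The case against.** The strongest reply is that the right analysis is already there. ITT is listed first, it counts every missed dose as non-compliance, and it answers the objective. Section 11.1 adds that p-values for secondary analyses are informational and support no definitive claim. Both points stand, and they limit the consequence to one misleading table and test beside a sound one. They give no reason to keep that table.

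A second reply is that the opening sentence covers efficacy, and compliance is not efficacy. The wording inside the section does distinguish the two comparisons. But the compliance test sits under the efficacy heading, and on this narrower reading it would have no stated population at all. Either reading calls for the same clarification.

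A third reply is that the SAP, which section 11.4 says will hold the details, may assign populations table by table. It may; it is not at hand, so an error in executed tables is not established. The protocol rule as written still gives the wrong set for this outcome.

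Four stronger readings are tempting and are not supported:
- *That the Evaluable analysis fixes compliance at 100%.* It does not. It conditions on one component of the outcome, and out-of-window dosing can still count against a subject.
- *That every subject who missed a dose is removed.* Section 11.4.4.1 keeps, as responders, subjects whose serological response was observed before they met an Evaluable exclusion. That clause is written for classifying response, but it might retain a few. If the exclusion is met when the dose is missed, the only scheduled follow-up sample that can precede a missed third dose is the Week 1 draw.
- *That most subjects who leave the study are removed as well.* Titers are required at the applicable follow-up visits, and no such visit is defined for compliance.
- *That the same sentence spoils the comparison of characteristics by HIV status, because subjects who acquire HIV leave the Evaluable set.* The protocol gives no seroconversion rate and does not say that these subjects are at higher risk than others. Requiring HIV-uninfected status to persist is a defensible way to keep the groups distinct, and the ITT version is planned there too.

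**Conclusion.** The concern holds for the Evaluable version of the compliance comparison, and for that alone. Its direction follows from the definitions: three-dose compliance is overstated by a factor of about 1/P(all doses received), with Arm 1 almost unaffected. Its size depends on dosing behaviour that the protocol does not state. Under the assumed rates it is 9.4 points (94.4 − 85) or 17.5 points (87.5 − 70). These figures rest on a fully compliant Arm 1, on negligible retention of subjects who missed a dose, and on the remaining Evaluable criteria being neutral. A reader might infer that the compliance objective goes unanswered; it does not, because the ITT analysis answers it. This is a modest defect in a stated rule, worth correcting because the correction is nearly free.

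**What to change.** In section 11.4.4.2, restrict the opening sentence on the two populations to the serological response analyses. In the compliance paragraph, add that compliance is analysed in the ITT population only, and delete the Evaluable version of that estimate, interval and test. Carry the same wording into the SAP if it repeats the general rule.

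The cost is about one sentence of text and one table fewer. Data collection, sample size, the primary analysis and the conduct of the trial are unchanged.
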